1. RELEVANCE, PROBLEM STATEMENT, AND SOLUTION

1.1 RELEVANCE OF THE TOPIC

Cardiovascular risk factors (CRF) have become a significant global health problem. In Chile, the National Health Survey (ENS) 2016-2017 reveals a high prevalence of cardiovascular risk factors, highlighting physical inactivity as one of the primary triggers.

The rise in cardiovascular risk factors among the Chilean adult population, both men and women, has become a priority issue requiring attention in current public policies. Evidence shows that the increase in these factors is directly associated with a higher risk of developing cardiovascular diseases, cerebrovascular diseases, and cancer.

According to the study conducted by Yusuf et al., which included 155,722 subjects from 21 countries, including Chile, approximately 70% of cardiovascular disease cases and deaths in the study were attributed to modifiable risk factors. Notably, individuals with low physical activity levels (less than 600 METs minutes per week) had a 20% higher risk of developing cardiovascular disease (Hazard Ratio [HR] of 1.20, 95% CI 1.10-1.30) and a 39% higher risk of mortality (HR 1.39, 95% CI 1.28-1.50), compared to those with high physical activity levels (more than 3000 METs minutes per week).

Regarding associated costs, in Chile, it is estimated that physical inactivity and its health consequences generate an expense of US\$ 103 million, with a direct cost of US\$ 69.2 million. The public sector covers 47.4% of these costs, while 31.7% fall on the users. The economic burden of physical inactivity represents between 1% and 3% of total annual healthcare costs. On the other hand, increasing moderate physical activity in sedentary adults can reduce direct medical costs by US\$ 300 to US\$ 1,053 per person per year.

Physically inactive adults have been observed to have a higher risk of hospitalization and surgery, often requiring stays in high-dependency or intensive care units. This stay in high-complexity services is associated with an increase in complications and related healthcare costs. Conversely, physically active users, if hospitalized or undergoing surgery, tend to experience a faster and less costly recovery.

Currently, there are primary healthcare initiatives for the control of cardiovascular risk factors, notably the Cardiovascular Health Program (CHP). This program aims to reduce the incidence of cardiovascular events by controlling and managing cardiovascular risk factors in primary healthcare. It offers a comprehensive approach, including free access to clinical controls, medications, and counseling on healthy lifestyles.

In terms of the relevance and currentness of the topic, it is important to highlight that 12,966,079 people are registered in one of the 1,890 primary health establishments nationwide. Of this population, 2,351,646 are under control in the CHP, with 873,835 (37%) men and 1,477,811 (63%) women. In the Los Ríos Region, approximately 300,000 users are registered in primary care establishments, of which 60,102 are under control in the CHP, with 22,892 (38%) men and 37,210 (62%) women. According to these data, 1 in 5 users in Chile and in the Los Ríos region is under control in the CHP, with a higher proportion of women. Regarding specific risk factors in the Los Ríos region, there are 50,291 users with hypertension, 22,669 with type 2 diabetes mellitus, and 35,980 with dyslipidemia, of which about 56% (1 in 2) have compensated factors.

In this context, it is essential to offer therapeutic alternatives for managing these cardiovascular risk factors that align with the National Health Strategy for the health objectives by 2030. This will reduce associated diseases, lower health costs, and improve the quality of life for these users. The national health strategy specifically seeks to improve lifestyles, increase the prevalence of physical activity in the population, prevent and reduce morbidity, disability, and premature mortality from non-communicable chronic diseases, reduce health inequalities arising from social and economic determinants, and strengthen health research.

Providing therapeutic strategies such as personalized physical exercise prescription for controlling cardiovascular risk factors in primary healthcare would advance towards a profile of healthier users with a better quality of life.

1.2 PROBLEM STATEMENT AND LITERATURE REVIEW

Over the past century, cardiovascular diseases (CVD) have evolved parallel to the epidemiological transition and global economic growth. By the end of the 20th century, CVD emerged as the leading cause of death and premature morbidity worldwide. This rapid change in the epidemiological profile, shifting from infectious diseases to cardiovascular diseases, can be attributed to a health transition marked by unchecked urbanization and the adoption of unhealthy lifestyles, resulting in a general decline in physical activity.

Currently, there is a concerning decline in physical activity levels globally, affecting all genders and ages. This situation is identified as a modifiable risk factor that can precipitate the onset of cardiovascular risk factors (CRF), which could be mitigated by increasing overall physical activity. Physical inactivity can trigger muscle insulin resistance and alter muscle fibers from oxidative to glycolytic, reducing the use of lipids as an energy source. These unmetabolized lipids accumulate in central and peripheral adipose tissues and organs as ectopic fat, increasing sympathetic activity and the inflammatory response, associated with a higher risk of Hypertension (HTN), Type 2 Diabetes Mellitus (DM2), and Dyslipidemia (DLP).

In addition to low physical activity levels, other factors such as abnormal lipids, smoking, HTN, DM2, and abdominal obesity constitute the majority of myocardial infarction risk globally, across all genders and ages. Approximately 70% of CVD cases and deaths in the general population could be attributed to modifiable risk factors. In Chile, a high prevalence of physical inactivity (86.7%) has been reported, correlating with an increase in CRF prevalence, especially in adults, and with considerable associated healthcare costs.

The 2017 National Health Survey revealed a high prevalence of CRF, including overweight, obesity, morbid obesity, and elevated levels of total cholesterol, LDL, and triglycerides, as well as HTN and DM2. These factors tend to concentrate from adulthood to old age. Regarding acute myocardial infarction (AMI), there is a high incidence, especially in older age groups.

In Chile, it has been identified that low socioeconomic and educational levels are social determinants of health that negatively impact, with higher rates of overweight, physical inactivity, hypertension, and diabetes observed in lower-income groups. These individuals often rely on the public health system.

Within the public health system, upon detecting these risk factors, individuals can access the Cardiovascular Health Program (CHP), which aims to reduce the incidence of cardiovascular events by controlling and compensating CRF in primary healthcare. This program offers comprehensive risk factor management, including access to clinical control, medications, and counseling on healthy lifestyles. Patients are classified according to their risk of having a cardiovascular event in the next ten years (CVR) as low, moderate, and high, with specific therapeutic goals set for each category.

Once the goals are defined according to the CVR level, a therapeutic management is established consisting of two phases: the compensation phase, aimed at achieving therapeutic goals, and the follow-up phase for the compensated patient. In the compensation phase, recommendations on healthy lifestyles are made, and

pharmacological treatment is prescribed according to the risk level. It is expected that in the first two to three months from joining the program and receiving medications, the patient will compensate their blood pressure, glycemia, glycated hemoglobin, and cholesterol levels. In the follow-up stage, controls are suggested according to an individualized intervention plan based on cardiovascular risk: high risk every 3 months, moderate risk every 6 months, and low risk every 6-12 months, either with a doctor, nurse, nutritionist, or senior nursing technician. Among the interventions to promote a healthy lifestyle, the promotion of regular moderate-intensity physical activity stands out.

The cardiovascular health program serves a wide range of users with various conditions, from individuals with only smoking habits to those who have suffered an acute myocardial infarction or have chronic kidney disease. This diversity poses a challenge in promoting physical activity for controlling and compensating CRF due to the multiple conditions associated with the users. Despite this, the benefits of physical exercise in controlling CRF and preventing cardiovascular diseases have been widely documented both globally and locally, showing a positive relationship between the volume of exercise performed and the benefits observed. In particular, primary prevention through the prescription of personalized physical exercise could control and compensate CRF, delaying the onset of pathologies such as acute myocardial infarction or chronic kidney disease, which is an important factor when evaluating the effectiveness of the CHP in compensating users, reducing the demand for care in the public health system, and lowering associated healthcare costs.

Locally, CESFAM Externo de Valdivia has 3764 users enrolled in the CHP, mostly from low socioeconomic backgrounds. The CHP promotes physical activity through counseling during scheduled check-ups, based on the technical guidelines of the CHP. The counseling, conducted by CHP professionals at all check-ups, consists of suggesting that users engage in regular moderate-intensity physical activity, without a defined dose or a mechanism for evaluating effectiveness, except for achieving the therapeutic goals defined upon joining the CHP. Thus, personalized physical exercise is not prescribed as an adjunct therapy to the CHP to improve the control and compensation of CRF in these users.

In this context, it has been reported that referral to physical exercise increases the likelihood of reaching a recommended level of physical activity to maintain health, with a relative risk (RR) of 1.16 [95% CI: 1.03 to 1.30] compared to usual care or simple counseling. Other studies have shown an increase of 55 minutes in weekly physical activity in users who were referred to an exercise program compared to those who only received counseling.

There are international success stories in this area, such as "Exercise is Medicine" in the United States, "Green Prescription Process for Primary Health Care" in New Zealand, the exercise prescription of the National Health Board in Sweden, and the "Exercise Referral" model in the United Kingdom. All these initiatives focus on improving the lifestyles of people with health conditions similar to CHP users, highlighting the written prescription of personalized physical exercise as an effective therapeutic measure for controlling CRF.

In Chile, specific exercise programs have been implemented to improve the quality of life and physical condition of adults with overnutrition, linked to the CHP. Notable examples are the "Cardiosalud" Program of the Ñuble Health Service, lasting seven months, and the Personalized Exercise Program of the Castro Municipal Corporation, lasting three months. Although results from these programs have not yet been published, in the Los Ríos Region, specifically in the commune of Los Lagos, positive effects of personalized physical exercise have been observed in CHP users at CESFAM Tomas Rojas, including the reduction of blood pressure, improvement of glycemia, lipid profile, and physical activity level.

Among the exercise modalities, concurrent exercise—which combines muscular strength and aerobic exercise in the same program—has proven effective in reducing CRF and improving physical capacity. The benefits include metabolic and morphological changes at the muscular level, such as mitochondrial biogenesis, the transformation of muscle fibers from fast to slow, and a more efficient substrate metabolism. Additionally, strength exercise promotes the synthesis of contractile proteins, increasing maximum strength. These changes favor the recovery of lost metabolic flexibility in these users, regulating the glycemic, lipid, and blood pressure profiles.

However, there is an underutilization of personalized physical exercise as a therapeutic strategy within the CHP of CESFAM Extero de Valdivia. Therefore, it is crucial to enhance CHP actions, integrating personalized physical exercise to promote better CRF control. This aligns with the strategic objectives of the National Health Strategy for 2030, including:

1. Prevention and reduction of morbidity, disability, and premature mortality from non-communicable chronic diseases, especially increasing the control of hypertension and diabetes mellitus.
2. Promotion of healthy habits and lifestyles, such as increasing the prevalence of physical activity.

3. Reduction of health inequalities, providing therapeutic strategies to reduce sedentary lifestyles, hypertension, and diabetes, especially in low socioeconomic CHP users in Valdivia.
4. Strengthening health research, proposing projects focused on evaluating the effectiveness of therapeutic interventions to address primary health issues in primary care, such as CRF control in the Cardiovascular Health Program.

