2.2.2 SPECIFIC OBJECTIVES

- Describe the effects of applying a personalized concurrent exercise prescription guide on cardiovascular risk factors in adult users of the Cardiovascular Health Program at CESFAM Externo de Valdivia.

- Describe the effects of applying a personalized concurrent exercise prescription guide on physical capacity in adult users of the Cardiovascular Health Program at CESFAM Externo de Valdivia.
- Evaluate adherence to the personalized concurrent exercise guide and pharmacological treatment in adult users of the Cardiovascular Health Program at CESFAM Externo de Valdivia.
- Describe the clinical significance of interventions through effect size calculation and perceived clinical relevance by participants regarding the interventions.

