- If the participant does not reach the mark, they will be asked to reduce the pace for a valid test without stopping the time.

Scoring: The score will be the total number of complete steps in 2 minutes, counted as the number of times the right knee reaches the set height. Only one attempt will be made on the test day.

Safety norms: Participants with balance issues should be near a wall or chair for support in case of balance loss. The examiner will supervise all participants for signs of excessive exertion. After the test, participants will walk slowly for one minute.

The equation to estimate peak oxygen consumption is: $VO_2 (\text{mLkg}^{-1}\text{min}^{-1}) = 13.341 + 0.138 * \text{total steps} - (0.183 * \text{BMI})$.

Body Composition: Height will be measured with a precision stadiometer (Seca Bodymeter 206), and weight, fat mass percentage, and lean mass percentage will be measured using a bioimpedance meter (TANITA BC-534). BMI will be estimated using the formula kg/m².

Treatment Adherence: Adherence to the treatment refers to the degree to which participants follow the prescribed physical exercise guide. This variable will be operationalized as compliance with at least 70% of the scheduled exercise sessions.

Measurement Method: Adherence will be measured using two primary mechanisms:

1. **Biweekly Phone Calls:** A follow-up protocol will be established, with calls made every two weeks to participants to gather self-reported compliance data with exercise sessions. These interactions will also identify potential barriers or facilitators of adherence, allowing proactive adjustments to the intervention if necessary.
2. **Exercise Logbooks Review:** Each participant will maintain a detailed logbook of exercise sessions performed, including date, duration, and type of exercise. Reviewing these records will provide an objective measure of adherence, complementing the data obtained through phone calls.

Adherence Criteria: A participant will be considered "adherent" if they comply with at least 70% of the scheduled exercise sessions, calculated by dividing the number of completed sessions by the total number of scheduled sessions and multiplying the result by 100.

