Global Rating Scale: The Global Rating Scale (GRS) will be applied as an essential instrument for evaluating the patient's perception of changes experienced in their health status, functionality, or symptoms. This evaluation will be conducted mainly at two key points: before and after the proposed clinical intervention.

The GRS methodology involves asking patients to provide a rating of their current health status compared to an established reference point, which, in our case, will be the study's start. This comparison will allow a quantitative and qualitative appreciation of the changes perceived by the patient.

To ensure a precise and adaptable evaluation, the GRS will be presented in two formats:

1. **Numerical:** Offering a range that can vary, for example, from -7 (much worse) to +7 (much better), allowing a gradable assessment of changes.

2. Descriptive: Providing qualitative terms such as "much worse," "no change," or "much better," facilitating patients' expression of change perception in a more narrative manner.

The GRS implementation will not only contribute to evaluating the intervention's effectiveness from the patient's perspective but also offer a valuable indicator of the clinical impact of the treatment. This patient-centered approach is fundamental for a comprehensive understanding of treatment outcomes, enabling adjustments and improvements in therapeutic strategies based on patient experiences and feedback.

Intervention

Experimental Group: Application of the exercise guide plus pharmacological treatment.

Exercise Guide Application: Cardiovascular Risk Classification for Exercise: Cardiovascular risk and physical capacity levels will be assessed using previously described procedures to provide a written personalized exercise protocol.

Exercise Protocol: According to the recommendations for exercise prescription for people with cardiovascular risk factors published by MINSAL, a protocol will be applied as follows:

- Protocol duration: 6 weeks.
- Frequency: 3 to 5 times per week.
- Exercise type: Concurrent, combining aerobic and muscular resistance exercises within the same program.

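### Exercise adherence is reduced to yes/no at 70% although the percentage of sessions is already calculated, so the adherence objective rests on one share with a 95% CI about 40 to 45 points wide

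*Combined protocol and SAP*

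**What the plan says.** Section 2.2.2 sets as its third specific objective: "Evaluate adherence to the personalized concurrent exercise guide and pharmacological treatment in adult users". This point concerns only the exercise part of that objective.

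Section 2.3, under Treatment Adherence, introduces adherence as a graded concept, then states: "This variable will be operationalized as compliance with at least 70% of the scheduled exercise sessions". The Adherence Criteria repeat the class. The percentage appears there only as the step that assigns it, "calculated by dividing the number of completed sessions by the total number of scheduled sessions and multiplying the result by 100". The raw material is richer than the class: "Each participant will maintain a detailed logbook of exercise sessions performed, including date, duration, and type of exercise".

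The prescription in section 2.3 gives "Frequency: 3 to 5 times per week" and "Protocol duration: 6 weeks".

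The Statistical Analysis paragraphs describe dependent variables by mean and standard deviation without naming adherence. The repeated-measures model contains Group, Time and their interaction, with no term for adherence or volume. No interval or precision target for adherence is given anywhere.

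Section 1.2 describes the exercise literature as "showing a positive relationship between the volume of exercise performed and the benefits observed". It does so as background; none of the four specific objectives asks for a dose-response analysis.

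**The concern.** This is a pilot of a written exercise guide, followed up by telephone every two weeks. How much of the guide people complete is therefore one of the main things it can teach. A yes/no class at 70% answers that coarsely. Someone who completes 20 of 30 sessions (67%) counts the same as someone who completes none, and 21 of 30 counts the same as 30 of 30. If the groups do not differ at six weeks, the adherent share gives only a rough basis for telling a guide that was not followed from one that was followed without effect.

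There is a second weakness. The percentage is relative to each person's own schedule, and schedules may differ, so neither the class nor the percentage measures the amount of exercise done.

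**Working it through.** **Inputs from section 2.3.** Total 39, allocation 1:1, target 15 per group, 30% dropout, cut at 70%, 3 to 5 sessions a week for 6 weeks. The plan states no precision for adherence, so there is no such figure to reproduce. Its total does follow from its own inputs: 2 × 15 × 1.3 = 39.

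**Assumptions not in the documents.** The adherent share, the standard deviation (SD) of the completion percentage, the correlation between completion and change, and normality of the completion percentage. Ranges are shown.

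1. *Size of the exercise arm.* 39 / 2 = 19.5, so 19 or 20 people.

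2. *Precision of the share* (Clopper-Pearson 95% interval):
   - 12/20 = 60%: 36.1% to 80.9%, width 44.8 points
   - 14/20 = 70%: 45.7% to 88.1%, width 42.4 points
   - 13/19 = 68%: 43.4% to 87.4%, width 44.0 points
   - 16/20 = 80%: 56.3% to 94.3%, width 37.9 points
   - if only 15 are counted, 10/15 = 67%: 38.4% to 88.2%, width 49.8 points

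3. *Information kept by the cut.* For a normal variable split so that a share p lies on one side, with z the corresponding normal quantile, the fraction kept is φ(z)² / [p(1 − p)].
   - p = 0.5: 0.637
   - p = 0.6: 0.622
   - p = 0.7: 0.576
   - p = 0.8: 0.490

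   The loss is therefore 36% to 51% over shares of 50% to 80%. It exceeds half only from about 80% upward. A completion percentage is bounded and may be skewed, so this is a guide to size only.

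4. *Precision of the mean percentage.* The half-width is t(0.975, n − 1) × SD / √n. At n = 20 it is 4.7, 9.4 and 14.0 points for an SD of 10, 20 and 30 points. At n = 15 it is 5.5, 11.1 and 16.6 points.

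5. *Percentage against amount.* 6 × 3 = 18 and 6 × 5 = 30 scheduled sessions. 13/18 = 72% is adherent; 20/30 = 67% is not, despite seven more sessions. The class, and the percentage too, can rank two people opposite to the sessions they did.

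6. *Relating completion to six-week change.* Simulated power at two-sided 5%, bivariate normal, assumed r = 0.5, 40,000 replicates:

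| n | uncut | cut, 50% adherent | cut, 70% adherent |
|---|---|---|---|
| 15 | 50% | 32% | 29% |
| 19 | 62% | 41% | 37% |
| 20 | 65% | 43% | 39% |

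   Even uncut, an observed r of 0.5 has a 95% CI (Fisher z) of −0.02 to 0.81 at n = 15 and 0.07 to 0.77 at n = 20. Such an analysis needs completers. A 30% loss from 39 leaves 39 × 0.7 = 27.3, or 13 to 14 per arm, so the row for 15 is if anything slightly favourable.

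**The case against.** The strongest reply is that nothing is thrown away. The percentage is calculated, the logbooks hold date, duration and type, and adherence is listed among the secondary variables. A mean and SD of the percentage would be compatible with the general descriptive sentence. That stands as far as the data go: the gap is in the planned analysis. It does not remove the point, because the general sentence does not name adherence, while the Treatment Adherence text expressly makes the variable a class.

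It is also fair to say that the wide interval comes mainly from the sample size, and that a share and a mean percentage are different estimands, so their interval widths cannot be set against each other as a gain in precision. Both stand. Keeping the percentage uses the information better but does not cure a small arm.

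A reader might go further and infer that the cut contradicts the protocol's rationale and destroys most of the volume-benefit relation. The documents do not support this. The clause in section 1.2 is literature background and no objective asks for the relation. It goes unexamined mainly because no such analysis is planned, cut or uncut. At adherent shares of 50% to 70% the cut keeps more than half of the information. The percentage of one's own schedule is not volume in any case.

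**Conclusion.** The point holds as a minor improvement in how adherence is defined and reported. The plan states a yes/no rule, plans no other adherence analysis, and so leaves the exercise part of its third objective with one share from 19 or 20 people. The widths rest on everyone in the exercise arm being counted and on the adherent shares shown; with fewer people counted they are wider. The information loss rests on normality.

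A reader might also infer that a null trial result could not be interpreted at all. That is too strong. The adherent share, the logbooks and the telephone calls about barriers all bear on whether the guide was followed; the class makes the reading coarse, not impossible. Nor would correlating completion with change settle it: power is only about 50% to 65% at 15 to 20 people even if r is 0.5, and the comparison is not randomised.

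**What to change.** In section 2.3, under Treatment Adherence:

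- Make the percentage of scheduled sessions completed the main adherence variable for the third specific objective. Report its mean with 95% CI, plus median and range, over everyone randomised to the exercise arm. State in advance how sessions are counted for participants who stop reporting.
- Report absolute sessions and minutes from the logbooks beside it, because schedules may run from 18 to 30 sessions.
- Keep the 70% share as a secondary summary with an exact 95% CI.
- Treat any analysis relating completion to six-week change as optional. If done, use the uncut percentage or session count and label it exploratory, non-randomised and low-powered.

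The cost is a few sentences and slightly more reporting. The percentage is already calculated and the logbooks are already planned. Settling this before analysis also removes a later choice between class and percentage once results are known.
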